8.4 Trial Groups

The subjects will be distributed among the different groups to receive CV7202 or Rabipur® (Table 8.1).

Table 8.1 Protocol CV-7202-104 Dose regimen

| | Trial Product | Composition | Dosing | | |
|--------------------------------|---------------|-------------|--------|-------|--------|
| | | | Day 1 | Day 8 | Day 29 |
| | | | N | N | N |
| Group 1 | Rabipur® | N/A | 10 | 10 | 10 |
| Group 2* | CV7202 | 5 µg mRNA | 10 | N/A | N/A |
| Group 3 • Group 3a** | | 1 µg mRNA | 16 | | 8 |
| Group 4 • Group 4a** | | 2 µg mRNA | 16 | | 8 |
| Total CV7202 | | | 42 | | 16 |

* Note that enrolment in Group 2 was already completed at the time this protocol amendment was issued.

** 'a' groups are a subset consisting of 8 subjects of Groups 3 and 4 scheduled to receive a first dose on Day 1 and a second dose on Day 29.

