10.3.5 Safety Analyses

The following safety and reactogenicity data will be summarized descriptively: vital signs, and vaccination site reactogenicity assessment.

The occurrence of solicited local and systemic AEs reported on the day of each vaccination and the 7 subsequent days and unsolicited AEs reported on the day of each vaccination and the 28 subsequent days will be presented.

The safety measurements will include:

1. AEs (type, intensity, frequency and relationship to vaccination), i.e. incidence and severity of AEs for both solicited local and systemic events (occurring on the day of vaccination and the 7 subsequent days) and unsolicited events (occurring on the day of vaccination and the 28 subsequent days).
2. SAEs, MAAEs and AEs leading to trial or vaccine withdrawal up to 12 months post last dose. After Visit 15 (Month 12), only SAEs and MAAEs that according to the

investigator are considered to be related to study vaccination will be collected.

3. Intercurrent medical conditions and AESIs throughout the trial.
4. Local reactogenicity assessment of injection site in all subjects.

Further, the incidence of AEs will be summarized in frequency tables by Medical Dictionary for Regulatory Activities (MedDRA) terms (system organ class [SOC] and preferred term [PT]). AEs that are reported as related to the test vaccine will be considered trial vaccine-related; missing classifications concerning trial vaccine relationship will also be considered trial vaccine-related.

Concomitant medications and vaccinations will be coded and summarized. Physical examination data will be listed.

Clinical laboratory test results with values below/above the reference range will be counted.

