6.4 Interim Analysis and Data Monitoring

One or more interim analyses (IAs) may be performed for this trial. The data will be cleaned for all subjects. The analyses will be based on a data snapshot. Analyses will be performed on the safety set or subsets of it based on the availability of data. No decision-making is planned for the IAs and no adjustments for the trial are planned based on the results.

It is not planned to discuss any difference between the IAs and the final analysis in the clinical trial report.

A first interim analysis was performed after 16 subjects had been vaccinated (10 subjects in the CV7202 5 µg group and 6 subjects in the Rabipur group) and observed until Visit 8. The first interim analysis focused on safety aspects only. It was planned in a standalone interim analysis plan, which was finalized on 6 February 2019.

The second interim analysis was performed after 53 subjects had been vaccinated (16 subjects in the CV7202 1 µg group, 16 subjects in the CV7202 2 µg group, 10 subjects in the CV7202 5 µg group and 11 subjects in the Rabipur group) and observed until Visit 12 (Day 57). The second interim analysis focused on safety and immunogenicity. The analysis was primarily based on the interim analysis plan as of 06 February 2019 and subsequent change requests for tables.

For details of data monitoring please refer to section 4.

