11.2.2 Unsolicited Adverse Events

Serious AEs, intercurrent medical conditions, AEs leading to trial or vaccine withdrawal, AEs of special interest (AESIs) and MAAEs will be collected by the investigator in the eCRF throughout the trial.

AEs with a suspected potential immune-mediated disease etiology will be considered AESIs. The investigator will assess if an AE is an AESI. A list of AESIs is provided in Appendix 10 of the protocol.

AEs that are reported as related to the test vaccine will be considered trial vaccine-related; missing classifications concerning trial vaccine relationship will also be considered trial vaccine-related.

Every unsolicited AE will be assigned to a vaccination dose (number) by consideration of the period of 28 days after vaccination administration. Unsolicited AEs can be assigned to either day 1 to 28 (dose 1 for any vaccination group), or day 29 to 57 (dose 2 for 2-dose regimens or dose 3 for the Rabipur group). For the Rabipur group, vaccination dose 2 is administered 8 days after vaccination dose 1, therefore no assignment of unsolicited AEs to vaccination dose 2 is done for the Rabipur group.

All AE summaries will be restricted to those AEs that occurred after the first administration of the trial product. Any other AE (ie, AE starting after trial entry and before the first vaccination) will be reflected only in the data listings. If it cannot be determined whether the AE occurred after the first administration of the trial product due to a partial onset date, then it will be counted as such. Verbatim terms in the eCRFs will be mapped to preferred terms (PTs) and system organ classes (SOCs) using the Medical Dictionary for Regulatory Activities (version 21.0 or higher).

The occurrence of unsolicited AEs reported on the day of vaccination and the 28 subsequent days will be presented. In addition selected AE summary tables will be repeated for unsolicited AEs occurring at any time after the first administration of the trial product.

Each AE summary will be displayed by vaccination group and dose regimen. Summaries by vaccination dose (number) will also be provided for all AEs. Summaries that are displayed by SOC and PT will be ordered by descending order of incidence of SOC and PT within each system organ class. Summaries will display number and percentage of subjects with at least 1 event and the number of events by vaccination group.

Summaries of the following types will be presented:

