Related serious adverse events	xx (xx.x%) xxx	xx (xx.x%) xxx	xx (xx.x%) xxx	xx (xx.x%) xxx
Medically attended adverse events	xx (xx.x%) xxx	xx (xx.x%) xxx	xx (xx.x%) xxx	xx (xx.x%) xxx
Adverse events leading to withdrawal from study	xx (xx.x%) xxx	xx (xx.x%) xxx	xx (xx.x%) xxx	xx (xx.x%) xxx
Adverse events leading to discontinued vaccination	xx (xx.x%) xxx	xx (xx.x%) xxx	xx (xx.x%) xxx	xx (xx.x%) xxx
Adverse events of special interest	xx (xx.x%) xxx	xx (xx.x%) xxx	xx (xx.x%) xxx	xx (xx.x%) xxx

n = Number of subjects; m = Number of events;

AEs on the day of vaccination and 28 subsequent days, but before dose 2 CV7202 or dose 3 of Rabipur.

Subjects reporting more than 1 event are counted only once for the subject count.

Percentages are based on total no. of subjects in each vaccination group.

Related: Adverse events which were assessed by the investigator as related to trial vaccine or study procedure.

PROGRAM SOURCE: tlf-###, DATA CUT OFF DATE: DDMMYYYY

RUN DATE: DDMMYYYY hh:mm

Programming note:

According to the SAP all unsolicited AE tables will be restricted to adverse events that occurred AFTER the first administration of the trial vaccine. If adverse events BEFORE are documented, these will be flagged and listed only. AEs on the day of vaccination and 28 subsequent days, but before dose 2 CV7202 or dose 3 of Rabipur.

Sponsor

Clinical Study Report

Page x of y

Protocol number

14.3.1.2.3 Overall Summary of Unsolicited Adverse Events Within 28 Days Post Dose 2 CV7202 or Dose 3 Rabipur, Safety Analysis Set

Adverse Event Category [n (%) m]	CV7202 2x1 µg (N = xx)	CV7202 2x2 µg (N = xx)	Rabipur (N = xx)
All unsolicited adverse events	xx (xx.x%) xxx	xx (xx.x%) xxx	xx (xx.x%) xxx
Related unsolicited adverse events	xx (xx.x%) xxx	xx (xx.x%) xxx	xx (xx.x%) xxx
Serious adverse events	xx (xx.x%) xxx	xx (xx.x%) xxx	xx (xx.x%) xxx
Related serious adverse events	xx (xx.x%) xxx	xx (xx.x%) xxx	xx (xx.x%) xxx
Medically attended adverse events	xx (xx.x%) xxx	xx (xx.x%) xxx	xx (xx.x%) xxx
Adverse events leading to withdrawal from study	xx (xx.x%) xxx	xx (xx.x%) xxx	xx (xx.x%) xxx
Adverse events leading to discontinued vaccination	xx (xx.x%) xxx	xx (xx.x%) xxx	xx (xx.x%) xxx
Adverse events of special interest	xx (xx.x%) xxx	xx (xx.x%) xxx	xx (xx.x%) xxx

n = Number of subjects; m = Number of events;

AEs on the day of vaccination and 28 subsequent days

Subjects reporting more than 1 event are counted only once for the subject count.

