14.3.1.2.6 Unsolicited Adverse Events Within 28 Days Post Dose 1, Safety Analysis Set

System organ class Preferred term [n (%) m]	CV7202 (N = xx)	CV7202 (N = xx)	CV7202 (N = xx)	Rabipur (N = xx)	Total (N = xx)
Any adverse events	xx (xx.x%) xxx	xx (xx.x%) xxx			
System organ class 1	xx (xx.x%) xxx	xx (xx.x%) xxx			
Preferred term 1	xx (xx.x%) xxx	xx (xx.x%) xxx			
Preferred term 2	xx (xx.x%) xxx	xx (xx.x%) xxx			
Preferred term 3	xx (xx.x%) xxx	xx (xx.x%) xxx			
Preferred term 4	xx (xx.x%) xxx	xx (xx.x%) xxx			
...	xx (xx.x%) xxx	xx (xx.x%) xxx			
System organ class 2	xx (xx.x%) xxx	xx (xx.x%) xxx			
Preferred term 1	xx (xx.x%) xxx	xx (xx.x%) xxx			
Preferred term 2	xx (xx.x%) xxx	xx (xx.x%) xxx			
Preferred term 3	xx (xx.x%) xxx	xx (xx.x%) xxx			
...	xx (xx.x%) xxx	xx (xx.x%) xxx			

n = Number of subjects; m = Number of events;

AEs on the day of vaccination and 28 subsequent days, but before 2nd CV7202 or 3rd Rabipur vaccination.

Adverse events were coded using MedDRA version 24.1. At each level of summation (system organs class, preferred term) subjects reporting more than 1 event are included only once.

Table is sorted by descending subject count in the total column by system organ class and preferred term.

Percentages are based on total number of subjects in each vaccination group

PROGRAM SOURCE: tlif-###, DATA CUT OFF DATE: DDMMYYYY

RUN DATE: DDMMYYYY hh:mm

Programming note:

Sort by decreasing frequency of the total column by SOC and preferred term.

According to the SAP all unsolicited AE tables will be restricted to adverse events that occurred AFTER the first administration of the trial vaccine (post vaccination). If adverse events BEFORE are documented, they will be flagged and listed only.

Sponsor

Clinical Study Report

Protocol number

Page x of y

14.3.1.2.7 Unsolicited Adverse Events Within 28 Days Post Dose 2 CV7202 or Dose 3 Rabipur, Safety Analysis Set

System organ class Preferred term [n (%) m]	CV7202 2x1 µg (N = xx)	CV7202 2x2 µg (N = xx)	Rabipur (N = xx)	Total (N = xx)
Any adverse events	xx (xx.x%) xxx	xx (xx.x%) xxx	xx (xx.x%) xxx	xx (xx.x%) xxx
System organ class 1	xx (xx.x%) xxx	xx (xx.x%) xxx	xx (xx.x%) xxx	xx (xx.x%) xxx
Preferred term 1	xx (xx.x%) xxx	xx (xx.x%) xxx	xx (xx.x%) xxx	xx (xx.x%) xxx
Preferred term 2	xx (xx.x%) xxx	xx (xx.x%) xxx	xx (xx.x%) xxx	xx (xx.x%) xxx
Preferred term 3	xx (xx.x%) xxx	xx (xx.x%) xxx	xx (xx.x%) xxx	xx (xx.x%) xxx

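### In the two unsolicited-AE tables titled Post Dose 1, the Rabipur column covers two injections while each CV7202 column beside it covers one

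*SAP*

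**What the plan says.** **Rule.** SAP 11.2.2 attributes each unsolicited AE to a dose by date: "Unsolicited AEs can be assigned to either day 1 to 28 (dose 1 for any vaccination group), or day 29 to 57". The second period belongs to Dose 2 in the two-dose CV7202 regimens and to Dose 3 for Rabipur. On the middle Rabipur dose, the section gives as its reason that "vaccination dose 2 is administered 8 days after vaccination dose 1" and concludes: "therefore no assignment of unsolicited AEs to vaccination dose 2 is done for the Rabipur group".

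**Shells.** The footnote of Table 14.3.1.2.2 reads: "AEs on the day of vaccination and 28 subsequent days, but before dose 2 CV7202 or dose 3 of Rabipur". The shell headed "14.3.1.2.6 Unsolicited Adverse Events Within 28 Days Post Dose 1, Safety Analysis Set" carries an equivalent footnote. Both tables set a Rabipur column beside three CV7202 dose-level columns, and 14.3.1.2.6 adds a Total column. Table 14.3.1.2.2 also has a row for related unsolicited AEs.

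**Protocol.** Section 8.4 schedules all Group 1 subjects for Rabipur on Days 1, 8 and 29. Section 10.3.5 states that "unsolicited AEs reported on the day of each vaccination and the 28 subsequent days will be presented". Sections 9.4.8 and 9.4.9 follow unsolicited AEs after Rabipur Dose 2 up to Day 36.

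**Other tables.** Solicited AEs have separate tables after Doses 1, 2 and 3, each with a Rabipur column. No unsolicited-AE table shows Rabipur Dose 1 or Dose 2 alone.

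**The concern.** Unsolicited AEs within 28 days, overall and related, are a primary endpoint (Protocol 4.2, SAP 11.1), and Protocol 5.6 names Rabipur as the active control for safety. Among the 28-day tables, only the Post Dose 1 pair gives all arms a common calendar window. The after-any-dose tables mix one-dose and two-dose CV7202 subjects with three-dose Rabipur subjects. A reader who wants to set a first CV7202 dose against the control will therefore go to 14.3.1.2.2 and 14.3.1.2.6.

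In those tables the arms have the same observation time but not the same number of injections. If an injection itself causes unsolicited AEs, the second Rabipur injection adds to a column headed as though it followed one. The error runs one way: the control figure can rise and CV7202 can look relatively better. With no formal test planned, readers depend on titles and adjacent columns.

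**Working it through.** The plan gives no figure to reproduce, so the check counts days and injections and then illustrates the size.

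**Inputs**
- Rabipur injection days 1, 8 and 29: Protocol Table 8.1, row "Group 1 | Rabipur® | N/A | 10 | 10 | 10".
- CV7202: Day 1, with a second dose on Day 29 in 8 of 16 subjects in each of Groups 3 and 4 (same table).
- Dose 1 window, Days 1-28: SAP 11.2.2.
- Controls: 10 planned. SAP 6.4 reports "11 subjects in the Rabipur group" at the second interim analysis.
- Unsolicited-AE rates: none in the documents. The per-injection risk p below is an assumption, varied from 5% to 50%.

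**Counts**
1. Interval from Rabipur Dose 1 to Dose 2: 8 - 1 = 7 days (the SAP text says 8).
2. Injections within Days 1-28: one for CV7202, two for Rabipur.
3. Days in the window on or after Rabipur Dose 2: 28 - 8 + 1 = 21, and 21/28 = 75%. The other 7 days (25%) follow Dose 1 only.
4. Dose 2's own period is Day 8 plus 28 further days, so Days 8-36, or 29 days. Of these, 21 (Days 8-28) go to Post Dose 1 and 8 (Days 29-36) go to Dose 3.

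**Illustration.** Assume that both vaccines carry the same per-injection risk p of an unsolicited AE, that injections act independently, and that all such events start within Days 1-28. The expected CV7202 percentage is p, the Rabipur percentage is 1 - (1 - p)², and the gap is p(1 - p).

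| Assumed p | CV7202 | Rabipur | Gap (points) | Expected controls with an event, of 10: one injection vs two |
|---|---|---|---|---|
| 5% | 5% | 9.8% | 4.8 | 0.5 vs 0.98 |
| 10% | 10% | 19% | 9 | 1.0 vs 1.9 |
| 20% | 20% | 36% | 16 | 2.0 vs 3.6 |
| 30% | 30% | 51% | 21 | 3.0 vs 5.1 |
| 50% | 50% | 75% | 25 | 5.0 vs 7.5 |

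With 11 controls and p = 20%, the counts are 2.2 vs 3.96.

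**Background events.** If every arm also has a background chance b over the window, independent of injection, the two figures become 1 - (1 - b)(1 - p) and 1 - (1 - b)(1 - p)². The gap is (1 - b)p(1 - p), never larger than in the table and zero when p = 0. Background AEs alone create no difference.

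**Cutting Rabipur at Dose 2 instead.** A 7-day Rabipur column beside 28-day CV7202 columns would have 7/28 = 25% of the observation time. At a constant rate it would expect a quarter of the background events.

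**The case against.** The strongest defence is that the rule is stated, reasoned and footnoted. Rabipur's 28-day periods overlap, so a unique attribution is hard. The protocol accepts the overlap: under 9.4.9 the Rabipur Dose 1 diary runs to Day 29 and the Dose 2 diary to Day 36, so its own Dose 1 period runs past Dose 2. Protocol 10.3.5 can thus be read as asking for overlapping periods, and it does not require mutually exclusive tables by dose. A reader might infer that the SAP breaks that section, but the wording does not establish this.

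The likely vaccine reactions (local reactions, fever, headache, fatigue and so on) are solicited and already tabulated by dose. Only injection-caused events outside those terms are at issue, and nothing in the documents supports a high p for them. The AE and vaccination listings (16.2.7.1.1 and 16.2.5) would let a reader redo the attribution for about 10 subjects.

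A simple remedy, cutting every arm at its own next dose, would replace an imbalance in injections with one in observation time and could favour the control instead.

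All of this stands, and it limits the size of the problem and shapes the fix. It does not justify the title. The footnote gives a cut-off but never says that the Rabipur column includes events after Dose 2, and no other unsolicited-AE table separates the two doses.

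**Conclusion.** The point holds as a labelling and comparability fault in two tables on a primary safety endpoint. In 14.3.1.2.2 and 14.3.1.2.6, three quarters of the Rabipur Post Dose 1 window lies on or after a second injection, against one injection in each CV7202 column. The direction is known for injection-caused unsolicited AEs; the amount is not. The 5 to 25 points in the illustration rest wholly on assumed risks, equal for both vaccines and independent between injections. With 10 controls they correspond to about 0.5 to 2.5 subjects.

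A reader might infer more: that a planned comparison on the primary endpoint is biased, or that every event after Rabipur Dose 2 is charged to Dose 1. The documents support neither. The trial is non-randomized and descriptive, the primary objective is the safety profile of CV7202, and the stated stopping rules do not rest on this comparison. Events on Days 29-36 go to Dose 3. Solicited AEs and constant-rate background AEs are untouched.

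**What to change.** 1. In SAP 11.2.2 and both shells, label the Rabipur column 'Doses 1 and 2, Days 1-28', and state that it includes events after the Day 8 injection.
2. Add one row, or one small table, for all arms with onset before any second injection: Days 1-7, cut at each Rabipur subject's actual Dose 2 date, since the Day 8 visit may fall one day late. This is the like-for-like single-injection comparison.
3. If Rabipur Dose 1 and Dose 2 are also shown separately, state the window lengths (about 7 and 21 days) and do not set them against 28-day CV7202 columns.
4. While editing the paragraph, correct the interval to 7 days.

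The cost is a few lines of SAP text and changes to two shells; onset and vaccination dates are already collected. The downside is that the single-injection comparison covers only 7 days and misses later-onset events. The relabelled column keeps the full-period figure.

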The occurrence of AEs (serious and non-serious) will be assessed by non-directive questioning of the subject at each visit. AEs volunteered by the subject during or between visits as subject diary card entries or detected through observation, physical examination, laboratory test, or other assessments during the entire trial, will be documented. Subjects will be instructed that they must immediately report any AEs with serious symptoms, subjective complaints or objective changes in their well-being to the investigator or the clinic personnel, regardless of the perceived relationship between the event and the test vaccine.

SAEs, MAAEs and AEs leading to trial or vaccine withdrawal will be collected up to 12 months after the last dose administration. After Visit 15 (Month 12), only SAEs and MAAEs that according to the investigator are considered to be related to study vaccination will be collected.

Intercurrent medical conditions and AESIs will be collected throughout the trial.

Clinical laboratory testing for safety evaluations are provided in Appendix 6. Definitions and procedures for recording, evaluating, follow-up and reporting of AEs are provided in Appendix 11.

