11.1 Safety Endpoints and Variables

The analysis of the primary objective to assess the safety and reactogenicity profile will examine solicited and unsolicited adverse events.

The primary endpoints include the following:

- The percentages of subjects with, and the frequencies and intensities of solicited local AEs reported on the day of vaccination and the 7 subsequent days (Days 1-8).
- The percentages of subjects with, and the frequencies, intensities, and relationship to vaccination of solicited systemic AEs reported on the day of vaccination and the 7 subsequent days (Days 1-8).
- The duration (in days) of solicited local AEs, of solicited systemic AEs, and of the individual solicited AEs.
- The percentages of subjects with and frequencies and intensities of any unsolicited and related unsolicited AEs reported on the day of vaccination and the 28 subsequent days (Days 1-29).

- The percentages of subjects with and frequencies and relationship to vaccination of any serious AEs (SAEs) and any medically attended AEs (MAAEs) up to 12 months after the last dose.
- The percentages of subjects with and frequencies and relationship to vaccination of any AEs of special interest (AESIs) up to 12 months after the last dose.

Secondary safety endpoints are:

- The percentages of subjects with and frequencies of SAEs and MAAEs related to study vaccination from 12 months after the last dose up to 24 months after the last dose (trial end).
- The percentages of subjects with and frequencies and relationship to vaccination of any AESIs from 12 months after the last dose up to 24 months after the last dose (trial end).

Further safety variables include the following:

- Extent of exposure
- Physical examination, weight, BMI
- 12-Lead electrocardiogram
- Vital signs
- Safety laboratory - hematology, biochemistry, coagulation
- Laboratory - Urine dipstick pregnancy test, serum pregnancy test (human chorionic gonadotropin)

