- Overall summary of unsolicited AEs that contain an overview of each item below
- All AEs
 - Mild (grade 1) AEs
 - Moderate (grade 2) AEs
 - Severe (grade 3) AEs
- Related AEs
 - Mild (grade 1) related AEs
 - Moderate (grade 2) related AEs
 - Severe (grade 3) related AEs
- SAEs
- Related SAEs
- MAAEs
- AEs leading to withdrawal from study
- AEs leading to discontinued vaccination

- AESIs

Laboratory data will be graded by the site in the AE form according to the United States Food and Drug Administration toxicity grading scale and the Common Terminology Criteria for Adverse Events Version 5.0.

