12. CHANGES TO PROTOCOL-SPECIFIED ANALYSES

The protocol defines 2 PP sets as subsets of the FA set. Due to the small number of subjects per treatment group, it was decided that no per-protocol sets will be defined and used for analysis.

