Preferred term 4	xx (xx.x%) xxx	xx (xx.x%) xxx	xx (xx.x%) xxx	xx (xx.x%) xxx
...	xx (xx.x%) xxx	xx (xx.x%) xxx	xx (xx.x%) xxx	xx (xx.x%) xxx
System organ class 2	xx (xx.x%) xxx	xx (xx.x%) xxx	xx (xx.x%) xxx	xx (xx.x%) xxx
Preferred term 1	xx (xx.x%) xxx	xx (xx.x%) xxx	xx (xx.x%) xxx	xx (xx.x%) xxx
Preferred term 2	xx (xx.x%) xxx	xx (xx.x%) xxx	xx (xx.x%) xxx	xx (xx.x%) xxx
Preferred term 3	xx (xx.x%) xxx	xx (xx.x%) xxx	xx (xx.x%) xxx	xx (xx.x%) xxx
...	xx (xx.x%) xxx	xx (xx.x%) xxx	xx (xx.x%) xxx	xx (xx.x%) xxx

n = Number of subjects; m = Number of events;

AEs on the day of vaccination and 28 subsequent days.

Adverse events were coded using MedDRA version 24.1. At each level of summation (system organs class, preferred term) subjects reporting more than 1 event are included only once.

Table is sorted by descending subject count in the total column by system organ class and preferred term.

Percentages are based on total number of subjects in each vaccination group

PROGRAM SOURCE: tlif-###, DATA CUT OFF DATE: DDMMYYYY

RUN DATE: DDMMYYYY hh:mm

Programming note:

Sort by decreasing frequency of the total column by SOC and preferred term.

According to the SAP all unsolicited AE tables will be restricted to adverse events that occurred AFTER the first administration of the trial vaccine (post vaccination). If adverse events BEFORE are documented, they will be flagged and listed only.

Sponsor

Clinical Study Report

Page x of y

Protocol number

14.3.1.3.1 Overall Summary of Unsolicited Adverse Events for the Duration of the Trial After any Dose, Safety Analysis Set

Adverse Event Category [n (%) m]	CV7202 1 µg (N = xx)	CV7202 2 µg (N = xx)	CV7202 5 µg (N = xx)	Rabipur (N = xx)
All unsolicited adverse events	xx (xx.x%) xxx	xx (xx.x%) xxx	xx (xx.x%) xxx	xx (xx.x%) xxx
Related unsolicited adverse events	xx (xx.x%) xxx	xx (xx.x%) xxx	xx (xx.x%) xxx	xx (xx.x%) xxx
Serious adverse events	xx (xx.x%) xxx	xx (xx.x%) xxx	xx (xx.x%) xxx	xx (xx.x%) xxx
Related serious adverse events	xx (xx.x%) xxx	xx (xx.x%) xxx	xx (xx.x%) xxx	xx (xx.x%) xxx
Medically attended adverse events	xx (xx.x%) xxx	xx (xx.x%) xxx	xx (xx.x%) xxx	xx (xx.x%) xxx
Adverse events leading to withdrawal from study	xx (xx.x%) xxx	xx (xx.x%) xxx	xx (xx.x%) xxx	xx (xx.x%) xxx
Adverse events leading to discontinued vaccination	xx (xx.x%) xxx	xx (xx.x%) xxx	xx (xx.x%) xxx	xx (xx.x%) xxx
Adverse events of special interest	xx (xx.x%) xxx	xx (xx.x%) xxx	xx (xx.x%) xxx	xx (xx.x%) xxx

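### No planned unsolicited-AE table matches the Month 12 primary or Month 12–24 secondary window for SAEs, MAAEs and AESIs, and none has a separate row for related MAAEs or related AESIs

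*SAP*

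**What the plan says.** **Endpoints.** SAP 11.1 lists as primary any SAEs and MAAEs, with relationship, up to 12 months after the last dose. AESIs have the same form: "frequencies and relationship to vaccination of any AEs of special interest (AESIs) up to 12 months after the last dose". The secondary safety endpoints begin where these stop. The first is worded "The percentages of subjects with and frequencies of SAEs and MAAEs related to study vaccination from 12 months after the last dose up to" (the sentence closes at Month 24), and the second covers AESIs with relationship over the same later period.

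**Tables.** SAP 11.2.2 presents unsolicited AEs on the day of vaccination and the following 28 days, and then says: "In addition selected AE summary tables will be repeated for unsolicited AEs occurring at any time after the first administration of the trial product". Its list of summary types starts with "Overall summary of unsolicited AEs that contain an overview of each item below". That list names related SAEs, but MAAEs and AESIs appear only undivided. The one shell that goes beyond 28 days and has SAE, MAAE and AESI rows is 14.3.1.3.1, "Overall Summary of Unsolicited Adverse Events for the Duration of the Trial After any Dose, Safety Analysis Set".

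**Collection.** Protocol 9.2 changes the rule partway through: "After Visit 15 (Month 12), only SAEs and MAAEs that according to the investigator are considered to be related to study vaccination will be collected". AESIs are not affected: "Intercurrent medical conditions and AESIs will be collected throughout the trial". SAP section 11 refers to protocol 9.2 for collection, yet SAP 11.2.2 describes SAEs and MAAEs as collected for the full length of the trial and does not mention the change.

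**The concern.** The endpoints are percentages of subjects and event frequencies within stated time windows. If the SAP is run as written, no output reports either window, and relationship is not shown separately for MAAEs or AESIs in any window. The secondary safety objective concerns only the period from 12 to 24 months, and no table isolates that period.

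The whole-trial SAE and MAAE rows raise a further problem. They add events of any cause from before the switch to related events only from after it. The result is, by definition, neither the primary nor the secondary endpoint, and without a footnote a reader could take it for a 24-month all-cause rate.

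**Working it through.** The documents give no numerical figure to reproduce. The check compares the SAP 11.1 endpoints with the Appendix C index and the Appendix D1 shells, and then sizes the effect.

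**1. Tables by window.**

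| Window | Tables | Number |
|---|---|---|
| 28 days | 14.3.1.2.1 to 14.3.1.2.7 | 7 |
| Whole trial | 14.3.1.3.1 to 14.3.1.3.5 | 5 |
| First dose to Month 12 | none | 0 |
| Month 12 to Month 24 | none | 0 |

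Total 7 + 5 = 12. No title, footnote or programming note cuts at Month 12.

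**2. How far the windows differ** (nominal days from the notes to protocol Table 2.1: Month 12 is Day 365 for one-dose groups and Day 393 for two-dose and Rabipur groups; Month 24 is Day 729 for all).

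- The 28-day tables cover 29/365 = 7.9% of the Month 12 window for one-dose groups, and 57/393 = 14.5% for the others.
- The whole-trial tables run past Month 12 by 729 − 365 = 364 days (364/729 = 49.9%) or 729 − 393 = 336 days (336/729 = 46.1%).
- Day 729 is 729 − 1 = 728 days after the last dose for one-dose subjects, but 729 − 29 = 700 days for two-dose and Rabipur subjects.

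**3. Rows.** SAP 11.1 implies 10 quantities. To Month 12 there are 3 event types × 2 (any, related) = 6. From Month 12 to 24 there are 4: related SAE, related MAAE, any AESI, related AESI. A table with the matching window exists for 0 of 10. Four of the 10 (related MAAE and related AESI, in each window) have no row of their own in any window. The four overall summaries (14.3.1.2.1, .2, .3 and 14.3.1.3.1) have a related-SAE row. Related MAAEs and related AESIs are counted only within the general row for related unsolicited events.

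**4. Which whole-trial rows mix collection rules.** The SAE and MAAE rows do. The related-SAE row and the AESI row do not, because those events are collected under one rule throughout; their only fault is the window.

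**5. Size, for MAAEs.** Let p be the proportion of a group with any MAAE up to Month 12, and r the proportion with a related MAAE afterwards. The documents give neither; assume p from 20% to 60% and r from 0 to 5%. The excess of the whole-trial row over the Month 12 figure is the proportion whose first counted MAAE comes after Month 12.

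- If later events are independent of earlier ones, excess = (1 − p) × r. At p = 40%, r = 2%: 0.60 × 0.02 = 1.2 points, and 0.012 × 16 = 0.19 of a subject in a group of 16. At p = 20%, r = 5%: 0.80 × 0.05 = 4.0 points, or 0.64 of a subject.
- Without independence, the excess lies between 0 and r, so at most 5 points: 0.05 × 16 = 0.8 of a subject.

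This bound applies to the count of subjects. The event count printed beside it rises by every related event after the switch, including those in subjects already counted.

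**The case against.** The strongest reply is that little is lost. The trial is descriptive, about 53 subjects were vaccinated, and listing 16.2.7.1.1 carries dates, relationship, and AESI and MAAE flags, so every quantity can be derived. SAEs also have their own listing and narratives. All of this stands, and it limits the point to tabulation. It does not remove the point, because a listing does not report percentages by group. SAP Appendix A allows tables to be split during programming but specifies no Month 12 cut, and SAP section 6 labels analyses done after finalisation as post hoc. A Month 12 table for a primary endpoint should not risk that label.

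A reader might infer more than the documents support:

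- *That these endpoints get no table at all.* Table 14.3.1.3.1 does show SAEs, related SAEs, MAAEs and AESIs to trial end. What is missing is a table with a matching window.
- *That endpoints were dropped without being declared.* The only entry in SAP section 12 begins "The protocol defines 2 PP sets as subsets of the FA set", but SAP 11.1 keeps every endpoint with its window. The list of shells is incomplete; no change was concealed.
- *That the protocol contradicts itself on when all-cause collection ends.* Note m to Table 2.1 and section 9.4.17 agree that the make-up Visit 15A repeats the Visit 15 procedures. Protocol 9.2 simply does not name 15A.
- *That AESIs fall into a 28-day gap.* Protocol 4.2 counts the primary AESI endpoint from vaccination, where the SAP says last dose. A gap arises only if the first dose is meant, and the paired secondary endpoint in the same section starts from the last dose.
- *That related counts are inflated.* Six shell footnotes extend related to study procedures, whereas SAP 11.2.2 and protocol Appendix 11 refer to the vaccine only. Whether this changes any count depends on the eCRF, which is not available here, and it has no bearing on the time window.

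**Conclusion.** The point holds. None of the 12 planned unsolicited-AE tables matches the Month 12 or the Month 12–24 window, and related MAAEs and related AESIs have no row of their own. The whole-trial SAE and MAAE rows combine two collection rules without saying so.

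The fault lies in the link from primary and secondary safety endpoints to planned output; no data are lost. The numerical effect on the MAAE percentage is likely small: 0 to 5 points, at most 0.8 of a subject in 16, given an assumed 0 to 5% risk of a related MAAE after Month 12. If no subject has a first counted event after the switch, the whole-trial and Month 12 percentages coincide. It is worth fixing because the correction is cheap and lets the trial report its own endpoints.

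**What to change.** Split table 14.3.1.3.1 in two:

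1. First dose to Month 12 after the last dose: SAEs, MAAEs and AESIs, each as any and related.
2. Month 12 to trial end: related SAEs, related MAAEs, and AESIs as any and related.

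State one cut that follows the collection switch: the Month 12 visit, including Visit 15A where it was held. The cut will then vary by subject. Month 12 is nominally 365 − 1 = 393 − 29 = 364 days after the last dose, so Visit 15 (±30) falls at 334 to 394 days and Visit 15A (+31 to +90) at 395 to 454 days. Say that the second window ends at nominal Day 729, which is 700 days after the last dose for two-dose and Rabipur subjects.

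Footnote the change in collection rule on any whole-trial SAE or MAAE row that is kept, and bring the SAP 11.2.2 sentence on collection into line with protocol 9.2.

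Two minor, separate items: align the protocol's wording of the primary AESI endpoint with the SAP's last-dose anchor, and check the study-procedure footnote against the eCRF and the vaccine-only rule.

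The cost is SAP wording, one cut rule, two added row types and footnotes. All the data are already collected.
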